9.4.1.4 HCV RNA Sample

HCV RNA sample – the following needs to be documented:

- **Quantitative HCV RNA by PCR test**
 - Test name and result in IU/mL

Confidential Information

No use or disclose outside AbbVie is permitted without prior written authorization from AbbVie

Version 3.0 (22 Apr 2015) – country v 1.0 dated 26.06.2015

Page 28 of 61

- Lower limit of detection (LLoD) **in IU/mL** and lower limit of quantification (LLoQ) **in IU/mL**
- **Qualitative** HCV RNA by PCR test
 - Test name and result (**positive/n gative**)
 - LLoD **in IU/mL**

9.4.1.5 Concomitant Medication

Concomitant medication - the following will be documented:

- Concomitant medication used from the time when the decision is made to initiate treatment with the ABBVIE REGIMEN until after the last dose

It should be verified by the treating physician that concomitant medication can be safely administered with the ABBVIE REGIMEN (including ritonavir) and RBV. Some medications may be contra-indicated, some may require dose adjustments due to potential for drug-drug interactions (DDIs). The investigator or qualified designee should review the concomitant medication(s) labels and screen concomitant medications at each visit for potential DDIs.

9.4.1.6 Standardized Assessment Tools

This study will assess quality of life and work productivity using PRO instruments: EQ-5D-5L and WPAI Hep C. Validated translations of these patient questionnaires will be administered.

Assessment of general quality of life - EQ-5D-5L

The EQ-5D-5L is a health state utility instrument that evaluates preference for health status (utility). The 5 items in the EQ-5D-5L comprise 5 dimensions (mobility, self-care, usual activities, pain/discomfort, and anxiety/depression) each of which are rated on 5 levels of severity. Responses to the 5 items encode a discrete health state which is mapped to a preference (utility) specific for different societies. Patients also rate their perception of their overall health on a separate visual analogue scale (VAS).

The EQ-5D-5L should require approximately 5 minutes to complete and is presented in Annex 1.

Confidential Information

No use or disclose outside AbbVie is permitted without prior written authorization from AbbVie

Version 3.0 (22 Apr 2015) – country v 1.0 dated 26.06.2015

Page 29 of 61

Assessment of work productivity and activity impairment – WPAI Hep C V2.0

The WPAI questionnaire will be used to measure work absenteeism, work presenteeism, and daily activity impairment. The WPAI questionnaire was created as a patient-reported quantitative assessment of both reduced productivity at work and non-work activities.

WPAI has been validated as a general health measure (WPAI-GH) and can be easily modified for specific health condition, disease or problem (WPAI-SHP). WPAI Hep C V2.0 is the HCV specific questionnaire that will be used in this study). Respondents are asked about time missed from work and time while at work during which productivity was impaired in the past seven days. Results of WPAI are expressed as a percentage of impairment from 0 to 100, with higher percentages indicating greater impairment and less productivity:

- % Presenteeism – percentage of impairment while working due to health problem
- % Absenteeism – percentage of work time missed due to health problem
- % Total work productivity impairment (TWP) – percentage of overall work impairment due to health problem
- % Total activity impairment (TAI) – percentage of general (non-work) activity impairment due to health problem

The WPAI Hep C should require approximately 5 minutes to complete and is presented in Annex 2.

PRO data are not considered a potential source of adverse reactions. However, participating sites should review the PRO data and if a possible product-related event (including a suspected adverse reaction) is noted, the health care provider (HCP) must determine whether the event is related to paritaprevir/r – ombitasvir ± dasabuvir (or any other AbbVie authorized product) and if so, it should be reported to AbbVie. The relevant AbbVie Pharmacovigilance contact details are specified in Section 11.0.

Patient Activation Measure – (PAM-13)

PAM 13 is a measure used to assess the patient knowledge, skill, and confidence for self-management. It should require approximately 7 minutes to complete and is presented in Annex 3.

Patient Support Program (PSP) Questionnaire

The PSP utilization and satisfaction assessment will evaluate the frequency of utilization and patient's overall satisfaction with their respective Patient Support Program.

The PSP questionnaire should require approximately 2-5 minutes to complete and is presented in Annex 5-6.

Confidential Information

No use or disclose outside AbbVie is permitted without prior written authorization from AbbVie

9.5 Study Size

In phase III studies investigating the interferon-free ABBVIE REGIMEN \pm RBV, SVR12 rates of at least 90% were observed, even in difficult-to-treat CHC patients (e.g. cirrhotic G1a treatment experienced patients). To describe in routine clinical practice the effectiveness of the ABBVIE REGIMEN \pm RBV in patients with CHC, a precise estimate of the SVR12 rates in the core population of this study should be achieved (see Section **Error! Reference source not found.** for the definition of the core population).

As obvious from Table 3, if the SVR12 rate is at least 90%, then with 158 evaluable patients the width of the 95% confidence interval (CI) will not be wider than 10%. If the SVR12 rate is at least 95%, then 94 patients are sufficient for a width of 10%. Therefore, 158 patients should be enrolled during the inclusion period of 8 months.

Table 3 Width of 95% Confidence Interval for SVR12

Number of patients	SVR12 rates	95% Confidence Interval*			Width
		Lower Limit	Upper Limit		
158	90%	84.2	94.2		10.0%
94	95%	88.4	98.4		10.0%

* exact two-sided 95% confidence interval according Clopper-Pearson

9.6 Data Management

9.6.1 Electronic Case Report Forms

Data for this study will be recorded in English by each participating center via an electronic data capture (EDC) system using a web-based eCRF. Examinations, diagnostic measures, laboratory assessments, findings and observations routinely performed in patients with CHC included in this cohort, will be transcribed by the investigator or designee from the source documents into the eCRF. Only data specified in the protocol will be entered into the eCRF. For each enrolled patient, the investigator or designee will create a new patient file in the eCRF and a unique patient number will be automatically allocated by the system.

A comprehensive data validation program utilizing front-end checks in the eCRF will validate the data. Automated checks for data consistency will be implemented, discrepancies need to be solved by the researcher in the eCRF before the module can be completed.

Confidential Information

No use or disclose outside AbbVie is permitted without prior written authorization from AbbVie

Version 3.0 (22 Apr 2015) – country v 1.0 dated 26.06.2015

Page 31 of 61

Follow-up on eCRF data for medical plausibility will be done by AbbVie personnel (or their representatives). Queries will be generated in the eCRF for online resolution at the site. The investigator or an authorized member of the investigator's staff will make any necessary data corrections to the eCRF. All change information, including the date and person performing the corrections, will be available via the audit trail, which is part of the EDC system. The principal investigator of each site will finally review the eCRFs for completeness and accuracy of available data and provide his or her electronic signature and date to the eCRFs as evidence thereof.

Access to the EDC system will be provided for the duration of the study through a password-protected method of internet access. Such access will be removed from investigator sites at the end of the site's participation in the study. Data from the EDC system will be archived on appropriate data media (e.g. CD-ROM) and provided to the investigator as a durable record of the site's eCRF data.

Original Questionnaires will be sent from the participating site to:

9.6.2

Assignment of Preferred Terms

AEs will be coded using the Medical Dictionary for Regulatory Activities (MedDRA) and will be tabulated by primary MedDRA system organ class (SOC) and preferred term (PT). For treatments, surgical and medical procedures the international non-proprietary name (INN) Drug Terms and Procedures Dictionary will be used.

9.7

Data Analysis

9.7.1

Analysis Population, Time Windows and Handling of Missing Data

The target population (TP) is defined as all patients who fulfill the criteria specified in Section 9.2.1. The core population (CP) is defined as all patients of the TP, who have started the treatment combination recommended in the current local label for their disease characteristics. Patients not receiving the treatment recommended in the local

Confidential Information

No use or disclose outside AbbVie is permitted without prior written authorization from AbbVie

Version 3.0 (22 Apr 2015) – country v 1.0 dated 26.06.2015

Page 32 of 61

label will be summarized in the non-core population (NCP). In addition, the core population with sufficient follow-up data (CPSFU) is defined as all CP patients, who fulfil one of the following criteria:

- (1) evaluable HCV RNA data ≥ 70 days after the last actual dose of the ABBVIE REGIMEN (i.e. data within the SVR12 time window)
- (2) a HCV RNA value ≥ 50 IU/mL at the last measurement post-baseline (i.e. no virological response achieved at the last measurement on-treatment or post-treatment)
- (3) HCV RNA < 50 IU/mL at the last measurement post-baseline, but no HCV RNA measurement ≥ 70 days after the last actual dose of the ABBVIE REGIMEN due to reasons related to safety (e.g. dropped out due to AE) or incomplete efficacy information (e.g. virologic failure such as relapse is reported in the eCRF but date and value of the corresponding HCV RNA test is missing). This means only patients who had virological response at their last on-treatment or post-treatment measurement, but had no HCV RNA measurements ≥ 70 days post-treatment for reasons not related to safety or effectiveness (e.g. lost-to-follow-up or patient not willing to perform an additional HCV RNA test ≥ 70 days post-treatment) will be excluded from this analysis.

The Safety Population (SP) is defined as all patients who received at least one dose of the ABBVIE REGIMEN.

In accordance with the non-interventional nature of the study all HCV RNA measurements will be performed at the sole discretion of the physician and all HCV RNA measurements have to be entered into the eCRF. All recorded HCV RNA values will be assigned to appropriate time points (baseline, on-treatment visits, EoT visit, post-treatment visits). The time windows for the assignments will be specified in the statistical analysis plan (SAP).

No data will be imputed for any effectiveness or safety analyses except for the analyses of the HCV RNA endpoints. When there is no HCV RNA value in a visit time window post-baseline, but prior to EoT, the closest values before and after the window, regardless of the value chosen for the subsequent and preceding window, will be used for the flanking imputation described below. If a patient has a missing HCV RNA value at a post-baseline visit prior to EoT but has undetectable HCV RNA (with LLoD ≤ 50 IU/mL) or unquantifiable, but detectable HCV RNA levels (with LLoQ ≤ 50 IU/mL) at both the preceding and succeeding measurements, the HCV RNA level will be considered undetectable or unquantifiable, respectively, at this visit for this patient. In addition, if a patient has an unquantifiable HCV RNA level at the preceding measurement and an

Confidential Information

No use or disclose outside AbbVie is permitted without prior written authorization from AbbVie

Version 3.0 (22 Apr 2015) – country v 1.0 dated 26.06.2015

Page 33 of 61

undetectable HCV RNA level at the succeeding measurement, or vice versa, the HCV RNA level will be imputed as unquantifiable at this visit for this patient. For virological response at EoT a corresponding backward imputation approach will be applied. This means if HCV RNA is missing at EoT, then unquantifiable or undetectable will be assumed for EoT, if the succeeding HCV RNA value is undetectable or unquantifiable. For SVR12 the single last available HCV RNA measurement ≥ 70 days post-treatment will be used. Subsequent to this flanking and backward imputation, if the HCV RNA value remains missing at a specific time point, then the patients will be considered as virological failure at this time point (i.e. not undetectable or unquantifiable).

9.7.2 Demographics and Disease Characteristics

All baseline and disease characteristics will be summarized for the CP stratified by the CP analysis groups (i.e. based on genotype 1 subtype, fibrosis status, treatment experienced or naïve), which are relevant for scheduled treatment combination (ABBVIE REGIMEN \pm RBV) and duration (12 and 24 weeks). In addition, baseline summaries will be repeated for the SP and the TP without stratification into subgroups. Summary statistics (n, mean, median, standard deviation [SD], and range) will be generated for continuous variables (e.g. age and body mass index [BMI]). The number and percentage of patients will be presented for categorical variables (e.g. gender and race). Further details of analysis populations and the CP analysis groups will be specified in the SAP, taking into account the ABBVIE REGIMEN recommended in the current local label for various patient groups.

9.7.3 Effectiveness Analysis

The primary effectiveness analysis on clinical outcomes will be performed on all patients in the CP stratified by the CP analysis groups. Due to the non-interventional nature of this study several different methods for determination of the HCV RNA value can be applied. For the purpose of the statistical analysis, a HCV RNA measurement is considered ≤ 50 IU/mL,

- if a PCR test was used
- and the test result is undetectable and the LLoD of the test is ≤ 50 IU/mL or the test result is unquantifiable and the LLoQ is ≤ 50 IU/mL

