analysis groups. Response rates (i.e. SVR12 rate, end of treatment [EoT] response rate, relapse rate, viral breakthrough) will be determined for the various CP analysis groups. The relapse rates will be estimated in patients of the CP analysis groups with EoT response and sufficient HCV RNA measurements post treatment. Viral breakthrough rates will be estimated in all patients of the CP analysis groups, who have at least one undetectable HCV RNA measurement on treatment and at least one on-treatment or EoT measurement thereafter. For all rates specified above 95%-confidence intervals (CIs) will be determined using the Clopper-Pearson method.

Univariate and multiple logistic regression (MLR) methods will be used to investigate the impact of various explanatory covariates (e.g. demographic and disease characteristics, co-morbidities, type of treating institution, and prior treatment for CHC and response outcome in treatment experienced patients) on SVR12. These analyses will be of exploratory nature, data driven, and will be performed for various CP analysis groups since not each covariate might be predictive in each patient group. Furthermore, the fact that treatment regimens will differ in the various patient groups has to be taken into account, when selecting the patient groups for each MLR analysis. Backward selection procedures will be applied to generate the final MLR models which will consider only covariates in the selection procedure with a p-value <0.25 in the corresponding univariate logistic regression analysis. A p-value <0.05 will be used for the covariates to stay in the model in a backward elimination step. Logistic regression methods will also be used to investigate the impact of treatment adherence on SVR12.

All safety variables will be summarized for patients in the SP using descriptive statistical methods stratified by the type of combination treatment and scheduled treatment duration.

Milestones:

Start of Data Collection:	Jan 2016
End of Data Collection:	Aug 2017
Final Report of Study Results:	May 2018

Confidential Information

No use or disclose outside AbbVie is permitted without prior written authorization from AbbVie

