## 6 Analysis populations

*The target population (TP)* – all patients, who fulfill the following criteria:

- treatment-naïve or treatment-experienced adult (age at least 18 years) male or female patients with confirmed CHC with genotype 1 (1a and/or 1b) only, receiving combination therapy with the interferon-free ABBVIE REGIMEN  $\pm$  RBV according to standard of care and in line with the current local label. The prescribed ABBVIE REGIMEN needs to be known;
- if RBV is co-administered with the ABBVIE REGIMEN, it has been prescribed in line with the current local label (with special attention to contraception requirements and contraindication during pregnancy);
- patients with voluntarily signed and dated a patient authorization to use and/or disclosure his/her anonymized health data (or informed consent) prior to inclusion into the study;
- patients must not be participating or intending to participate in a concurrent interventional therapeutic study.

Patients who prematurely discontinue earlier than  $\leq$ study day 55 (for 12 weeks treatment) or  $\leq$ study day 139 (for 24 weeks treatment) will be used in analyses on the population with actual EoT time point without windowing conventions adjustment for EoT.

*The core population (CP)* – all patients of the TP, who have started the treatment combination recommended in the current local label for their disease characteristics. Patients, who fulfill at least one of the following conditions, will be excluded from the CP:

- patients with unknown fibrosis status;
- cirrhotic patients with genotype 1a not receiving ribavirin;
- patients with genotype 1 for whom two direct-acting antiviral agents regimen (2DAA) instead of 3DAA is prescribed;
- patients with EoT  $\leq$ study day 55 (for 12 weeks treatment) or  $\leq$ study day 139 (for 24 weeks treatment).

*The safety population (SP)* – all patients who received at least one dose of the ABBVIE REGIMEN.

 This table is based on the table 4 “Analysis time windows” of clinical study Protocol.

 These time windows are intended for the CP allocation filter only. In case of the TP, all patients will be used for the analysis regardless of actual EoT day relevance to EoT time windows.

 This section is based on the sections 9.7.1 “Analysis population, time windows and handling of missing data” and 9.2.1 “Target population” of clinical study Protocol.

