## 9 Effectiveness analysis

Effectiveness analysis will be conducted on *the core population (CP)*, *the target population (TP)* and *the core population with sufficient follow-up data (CPSFU)*.

The results will be reported overall and for scheduled treatment combination ( $\pm$  RBV) and duration (12 or 24 weeks) groups. Additionally and only for *the core population (CP)* the results will be presented for the CP analysis groups by the following parameters:

- HCV genotype and subtype (1a or 1b);
- fibrosis status (the Child Pugh Score class: A, B or C);
- treatment experienced or naïve patients (with/without prior treatment for CHC).

Tables with descriptive statistics will be prepared in accordance with section 7.1. Confidence intervals will be presented according the section 7.2. All corresponding listings will be presented. Additional listings for *the non-core population (NCP)* will be created.

The following effectiveness endpoints will be analyzed:

- the percentage of patients achieving SVR12 (single last HCV RNA <50 IU/mL 12 weeks after the last actual dose of the ABBVIE REGIMEN);
- the percentage of patients with at least one and each of SVR12 non-response categories:
  - breakthrough (at least one documented HCV RNA <50 IU/mL followed by HCV RNA  $\geq$ 50 IU/mL during treatment);
  - failure to suppress (each measured on-treatment HCV RNA value  $\geq$ 50 IU/mL);

---

 Parameter “HCV Genotype and Subtype” from eCRF form “CHC DISEASE CHARACTERISTICS”.

 Parameter “Class” in section “Child Pugh Score” from eCRF form “Liver fibrosis stage”.

 Parameter “Prior treatment for CHC?” from eCRF form “MOST RECENT PRIOR THERAPY FOR CHC”.

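### The SAP neither defines the joint patient groups that stratify the protocol's primary SVR12 analysis nor plans an SVR12 table by them

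*Protocol*

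**What the plan says.** **Protocol.** Section 9.7.3 sets the primary analysis: "The primary effectiveness analysis on clinical outcomes will be performed on all patients in the CP stratified by the CP analysis groups". Section 9.7.2 describes the groups as "i.e. based on genotype 1 subtype, fibrosis status, treatment experienced or naïve), which are relevant for scheduled treatment combination" and duration. It leaves the details to the SAP, "taking into account the ABBVIE REGIMEN recommended in the current local label for various patient groups". The Abstract (Data Analysis) adds that SVR12, end-of-treatment response, relapse and breakthrough rates "will be determined for the various CP analysis groups", with Clopper-Pearson intervals for all of them.

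**SAP text.** Section 9 says "The results will be reported overall and for scheduled treatment combination" (with or without RBV) and duration. For the CP only, it adds that "the results will be presented for the CP analysis groups by the following parameters", followed by three bullets: subtype 1a or 1b, fibrosis status ("the Child Pugh Score class: A, B or C"), and prior treatment yes or no. It gives no rule on whether these are crossed. Section 6 excludes from the CP, among others, "cirrhotic patients with genotype 1a not receiving ribavirin". Section 16 declares the methods fully consistent with the protocol and names one departure, the dropped regression on the patient support program.

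**SAP shells (section 18).** Tables 1.4.2 to 1.4.4, and the matching EQ-5D tables, split by genotype, by Child-Pugh class and by prior treatment in separate tables. They then repeat each split within each regimen group. The regression tables (2.2.x) are repeated by RBV use, by Child-Pugh class and by treatment experience, each separately. The SVR12 tables (2.1.x) have regimen columns and Overall, repeated for other populations and with missing SVR12 left out. None is listed by subtype, fibrosis or prior treatment.

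**The concern.** The CP analysis groups are the strata of the primary analysis, not an optional subgroup look. The protocol chose the three factors because they bear on which combination a patient is scheduled to receive and for how long. The documents treat that as a joint matter: the SAP 6 exclusion turns on subtype together with cirrhosis, and Protocol 7.1 discusses duration in terms of cirrhosis, subtype and prior response together.

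If the SAP is executed as its shells stand, SVR12 will appear by regimen and overall. If the bullets in SAP 9 are followed on the pattern of the other shells, SVR12 will also appear for 1a against 1b, by Child-Pugh class, and for naïve against experienced patients. In neither case is there a row for, say, cirrhotic 1a patients. The study could then finish without the description by patient group that its primary analysis promises.

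**Working it through.** **1. The plan's own figure.** Protocol 9.5 (Table 3) gives 84.2 to 94.2, width 10.0 points, for 158 patients at 90%. The Clopper-Pearson limits for x successes in n are the 2.5% quantile of Beta(x, n−x+1) and the 97.5% quantile of Beta(x+1, n−x).

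- With x = 0.9 × 158 = 142.2: 84.23 to 94.20, width 9.97. The figure reproduces.
- With a whole count, 142/158: 84.08 to 94.10, width 10.02.

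This precision is for the pooled CP. Neither document states a precision for any group.

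**2. What each planned output shows.**

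| Output | Split | Joint subtype-by-cirrhosis group? |
|---|---|---|
| SVR12 shells, Tables 2.1.x | regimen, Overall | no |
| SAP 9 bullets | subtype; Child-Pugh class; prior treatment | not stated |
| Baseline and EQ-5D shells | one factor per table, overall and within regimen | no |
| Regression shells, Tables 2.2.x | RBV use; Child-Pugh class; experience | no, and no subtype split |

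**3. Can one-way rows recover the joint groups?** The documents give no group sizes, so these are assumed: 1a non-cirrhotic 20, 1a cirrhotic 12, 1b non-cirrhotic 86, 1b cirrhotic 40 (total 158), with 16 failures. Fix the one-way results:

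- 1a 26/32 (6 failures); 1b 116/126 (10 failures)
- non-cirrhotic 98/106 (8 failures); cirrhotic 44/52 (8 failures)

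Let f be the failures among cirrhotic 1a. The other cells follow: non-cirrhotic 1a has 6 − f, cirrhotic 1b has 8 − f, and non-cirrhotic 1b has 8 − (6 − f) = 2 + f. Every f from 0 to 6 fits the same one-way rows:

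| f | 1a cirrhotic | 1a non-cirrhotic | 1b cirrhotic | 1b non-cirrhotic |
|---|---|---|---|---|
| 0 | 12/12 (100%) | 14/20 (70.0%) | 32/40 (80.0%) | 84/86 (97.7%) |
| 3 | 9/12 (75.0%) | 17/20 (85.0%) | 35/40 (87.5%) | 81/86 (94.2%) |
| 6 | 6/12 (50.0%) | 20/20 (100%) | 38/40 (95.0%) | 78/86 (90.7%) |

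**4. Does repeating the rows within each regimen help?** Only in special cases. Within one regimen the same algebra leaves one free quantity whenever all four cells are occupied. If one cell is empty, the others follow by subtraction. The exclusions listed in SAP 6 do not guarantee an empty cell: they cover unknown fibrosis status, cirrhotic 1a without ribavirin, the two-agent regimen, and early end of treatment. The general CP definition (the combination recommended by the label) might, but the label is not reproduced. No SVR12 shell of this within-regimen kind is listed either.

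**5. Precision in joint groups.** Exact 95% intervals at or near 90%, assuming 158 patients split equally:

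| Cells | Count | Interval | Width |
|---|---|---|---|
| 4 | 36/40 | 76.3 to 97.2 | 20.9 |
| 8 | 18/20 | 68.3 to 98.8 | 30.5 |

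**The case against.** The strongest reply has five parts.

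- *The one-at-a-time reading is inferred.* SAP 9 says neither one-way nor crossed. This stands. The safe statement is that the groups are undefined and the SVR12 shells carry no version of them.
- *Regimen columns already represent the label groups.* CP patients are meant to be on the label-recommended combination, and SVR12 is reported by RBV use and duration. This stands in part. Cirrhotic and non-cirrhotic 1a patients can share a +RBV column, so the column does not identify the profile.
- *The baseline and EQ-5D shells repeat the splits within regimen.* True. Carried over to SVR12, this would reduce the mixing of regimens within a subtype row, but in general it would not separate the joint groups.
- *The protocol never requires crossing.* It says the groups are based on the three factors and leaves the details to the SAP. The SAP also cites protocol version 4.0, while the one supplied is version 3.0 (country version 1.0). So a breach of an explicit instruction cannot be shown. The task of defining the groups is still not done in the SAP.
- *The study is descriptive and the cells will be small.* Correct, and subtype and fibrosis measures do enter the SVR12 regressions. This argues for labelling the table descriptive, not for omitting it.

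A reader might infer that no output gives SVR12 in any group that decides the regimen. The documents do not support that: the label is not supplied, and the regimen columns are a partial proxy. Nor do they show that a low rate would be hidden in every reported row. In the example above, 1a at 26/32 (81%) already stands below 1b at 116/126 (92%). The 80% in Protocol 7.1 is not a benchmark for this gap either: it concerns cirrhotic 1a prior null responders treated for 12 weeks, not all cirrhotic 1a patients.

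**Conclusion.** The point holds in this limited form. The protocol makes label-relevant groups the strata of its primary SVR12 analysis. The SAP lists the factors without defining the groups, provides no SVR12 shell by them, and does not record this in section 16. The pooled estimate and its planned precision are unaffected. What is lost is the description by joint group: under the assumed sizes, the overall one-way rows leave SVR12 in cirrhotic 1a anywhere between 50% and 100%. That range depends on invented sizes and failure counts. The principle, that overall one-way rows do not generally fix the joint cells, does not. Reading the groups as joint is a reasonable inference from the protocol's stated purpose and from the SAP 6 rule, not an explicit instruction. This is a worthwhile and cheap improvement rather than a threat to the study's main result.

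**What to change.** 1. In SAP 9, define the CP analysis groups as subtype (1a, 1b) by cirrhosis (yes, no), split further by treatment experience where numbers allow. Take cirrhosis from the same status that the CP exclusion rule in SAP 6 already needs, and write down how it is derived. Child-Pugh class grades cirrhosis and has no non-cirrhotic level, so it cannot serve alone.
2. Add one SVR12 table for the CP by these groups, with n/N and Clopper-Pearson intervals, beside the overall CP rate. Label it descriptive.
3. Keep the one-way splits as supplementary.
4. State that the 10-point precision applies only to the pooled CP.

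The cost is one table and one written derivation rule, with no new data item if the cirrhosis status used in SAP 6 is available. The downside is small cells with wide intervals, which must not be read as evidence of differences between groups.
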